10.3.4 Safety Analyses

10.3.4.1 Adverse Events

For mothers, adverse events (AEs), including serious adverse events (SAEs), will be summarized by system organ class and preferred term using MedDRA (The Medical Dictionary for Regulatory Activities). Adverse events will be presented as the number and proportion of participants experiencing at least one incidence of each event and will be presented overall and by treatment

group. Listings of serious adverse events will be provided, sorted by treatment, system organ class, and preferred term. Detail in these listings will include severity, relationship to study drug, and outcome. The number of participants experiencing each type of AE and SAE may be compared between treatment arms using either Fisher's Exact test or Pearson's χ^2 test, as appropriate.

For infants, events will be summarized in a similar way, however, infant death, congenital anomalies in all infants and other infant SAEs in breastfed infants are reportable.

10.3.4.2 *The Hospital Anxiety and Depression Scale (HADS)*

Depression and anxiety scores, as measured by the HADS, will be summarized using descriptive statistics over time by treatment arm. Repeated measures mixed models may be used to compare the treatment groups on the depression and anxiety symptoms from screening/baseline through 12 months postpartum.

10.3.4.3 *Fetus/Delivery-Related Outcomes*

Fetus/delivery-related outcomes will be summarized by treatment arm. Listings may be provided for fetus- or delivery-related outcomes of particular concern and will be broken down by treatment arm.

10.3.4.4 *Birth/Neonatal Outcomes*

Outcomes related to the birth and/or neonate, such as head circumference or the need for resuscitation, will be summarized by treatment arm and listings may be provided for adverse outcomes, as needed.

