4.2 Rationale for Study Medications

4.2.1 CAM2038 vs. Sublocade™

Two BUP-XR products have been developed recently (CAM2038 from Braeburn Pharmaceuticals and Sublocade™ from Indivior), both of which are subcutaneously injected and form a gel deposit under the skin that releases BUP at a steady rate for up to one month; the CAM2038 product is also available as a weekly formulation. Sublocade™ received FDA approval in 2017. In 2018, the FDA determined that CAM2038 met all safety and efficacy standards necessary for approval but did not approve it for marketing due to exclusivity issues. The monthly formulations of both Sublocade™ and CAM2038 use N-methyl-2-pyrrolidone (NMP), a compound which animal studies suggest may have adverse fetal-infant effects, as an excipient.

The weekly CAM2038 product does not include NMP and, thus, was selected as the BUP-XR medication for MOMs. Specifically, the weekly CAM2038 product will be utilized while participants are pregnant or breastfeeding and the monthly formulation will be utilized during the postpartum phase for women who are not breastfeeding. The weekly CAM2038 product includes three excipients: 1) phosphatidylcholine; 2) glycerol dioleate (GDO); and 3) ethanol. The target weekly CAM2038 dose is 24 mg, but a minority of participants may require the highest dose (32 mg). The maximum potential exposure to the excipients for any participant/fetus would be for a pregnant woman randomizing into MOMs at 6 weeks EGA, delivering at 40 weeks, and receiving the maximum potential CAM2038 dose (32 mg of buprenorphine in 0.64 mL) every week. The maximum potential exposure to these excipients for any participant/breastfeeding infant postpartum would be for a participant receiving the 32 mg CAM2038 dose every week.

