4.3.2 Medication Check Visits vs. Research Visits

In a pragmatic trial, research assessments/interactions that could impact outcomes and, thus, reduce the generalizability of the results to real world practice are minimized. However, this goal must be balanced with the need to closely monitor safety given that CTN-0080 is the first trial to evaluate the BUP-XR formulation in pregnant women. This balance will be achieved by including weekly Medication Check Visits, which include a minimal number of assessments and procedures (see **Table 3**), while limiting more intensive data collection to Research Visits, which will occur less frequently (e.g., monthly during pregnancy, etc.; see **Table 3**).

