Infant Sedation: Infant sedation will be assessed via mother-report as outlined in **Table 3**. The infant sedation assessment will be completed by participants who are feeding their infants with breastmilk and/or formula and will assess for signs of infant sedation (e.g., not waking for feeding, difficulty breathing, etc.).

Bayley™-4. The Bayley™-4¹⁰² includes cognitive, language, fine motor, and gross motor subscales.

Child Behavior Checklist (CBCL). The CBCL¹⁷⁴ is administered to caregivers and includes items that describe behavioral, emotional, and social problems that characterize preschool children.

Events related to withdrawal symptoms will be captured on the SOWS-Gossop and will not be duplicate-reported on an AE form. However, precipitated withdrawal during study medication induction will be reported as an AE. Events captured on study specific forms (e.g., HADS) will not be recorded separately as an AE, unless they meet the SAE definition. Any of these events that meet the definition of an SAE, during the reporting periods described below, will be reported on the AE/SAE form set.

Adverse Events and Serious Adverse Events:

For the purpose of this study and if not described above, these events are required to be reported as an AE/SAE:

- All deaths that occur in either the Mother or the Infant (SAE)
- Congenital anomaly observed (SAE)
- Other infant SAEs that occur in breastfed infants
- All maternal AEs/SAEs while on study, except as noted below in “Events that do not require AE/SAE reporting”
- Maternal hospital re-admission within 6 weeks of delivery (SAE)
- Any ICU admission during the Labor and delivery admission (SAE)
- An opioid overdose resulting in naloxone rescue (SAE)

Events that do not require AE/SAE reporting:

- Hospitalization for Labor and Delivery, unless the hospitalization results in an ICU admission
- Prolongation of the hospital stay for a delivery (unless greater than 4 days for vaginal delivery or 7 days for C-section delivery)
- Admission to a hospital for elective surgery or pre-scheduled diagnostic tests
- Opioid overdose, unless resulting in naloxone rescue, hospitalization, or death
- Infant AEs and SAEs, except infant deaths, congenital anomalies in all infants, , and other infant SAEs in breastfed infants

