Any adverse event is considered "unexpected" if it is not listed in the investigator's brochure or the package insert or is not listed at the specificity or severity that has been observed. If neither is available, then the protocol and consent are used to determine an unexpected adverse event.

Medical and Psychiatric History

A thorough medical and psychiatric history during the baseline phase should record any chronic, acute, or intermittent preexisting or current illnesses, diseases, symptoms, or laboratory signs of

the participant, to avoid reporting pre-existing conditions as new AEs and to assist in the assessment of worsening in intensity or severity of these conditions that would indicate an AE. Stable chronic conditions, such as arthritis, which are present prior to clinical trial entry and do not worsen are not considered AEs.

Site's Role in Eliciting and Reporting Adverse Events

Appropriately qualified and trained personnel will elicit participant reporting of AEs and SAEs at each study visit designated to collect AEs. Adverse events (medical and/or psychiatric) assessment will initiate with participant consent and follow-up of reported AEs will continue through 30 days post last study visit. Study personnel will obtain as much information as possible about the reported AE/SAE to complete the AE/SAE forms and will consult as warranted.

Standard reporting, within 7 days of the site becoming aware of the event, is required for reportable AEs. Expedited reporting (within 24 hours of their occurrence and/or site's knowledge of the event) is required for reportable SAEs (including death and life-threatening events). Local sites are responsible for reporting SAEs to the IRB of record, per the IRB of record's guidelines.

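### The maternal adverse event summary is not split by pregnancy and postpartum or by BUP-XR formulation, so a general maternal harm confined to pregnancy may be diluted

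*Combined protocol and SAP*

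**What the plan says.** Section 10.3.4.1 (Adverse Events) has maternal events coded by system organ class and preferred term and "presented as the number and proportion of participants experiencing at least one incidence of each event", overall and by arm. Testing is optional: "The number of participants experiencing each type of AE and SAE may be compared between treatment arms", by Fisher's exact or Pearson's chi-square test. For the SAE listings, "Detail in these listings will include severity, relationship to study drug, and outcome"; onset phase and formulation are not named.

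The section states no counting window, so it has to be read from elsewhere. Section 11.17.2 makes reportable "All maternal AEs/SAEs while on study, except as noted below" in a list of exceptions. Appendix A (section 16.0) says that AE "assessment will initiate with participant consent and follow-up of reported AEs will continue through 30 days post last study visit". Section 8.5 runs active treatment through about 12 months after delivery.

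The BUP-XR product can change at delivery. Under section 4.2.1 the weekly product is used in pregnancy and breastfeeding, and "the monthly formulation will be utilized during the postpartum phase for women who are not breastfeeding". The monthly product contains the excipient NMP; the weekly one does not.

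Other outcomes do have a time dimension. Section 10.1.2 lists adherence, drug-negative urines and craving separately for pregnancy and postpartum, and section 10.3.4.2 summarizes the HADS over time.

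**The concern.** Section 4.3.2 justifies close safety monitoring on the ground that "CTN-0080 is the first trial to evaluate the BUP-XR formulation in pregnant women". Maternal AE rates during pregnancy are therefore much of the new safety information, yet no planned table shows them. In an at-least-one-event count over the whole study, a woman with an event in pregnancy and a woman with the same event ten months after delivery count alike. Once a woman has the event in either phase, she adds nothing further to the contrast.

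Two things are at stake. A difference between arms that arises only in pregnancy may look smaller than it is. In addition, the BUP-XR column combines two products, so a difference seen there cannot be assigned to the one used in pregnancy. If the phase split is left until the results by arm are known, it becomes a post hoc choice.

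**Working it through.** **The plan's own figure.** The only power figure in the documents is Table 8, for the primary non-inferiority test. With margin 0.15, variance 0.11 per arm and one-sided 2.5%, power = Φ(0.15/√(4 × 0.11/N) − 1.96). This gives 85.1% at N = 176 and 89.2% at N = 200, against the stated 84.9% and 89.0%. Table 8 reproduces, but it has no bearing on the AE summary, for which no figure is given.

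**Share of follow-up.** Randomization is at 6 to 30 weeks EGA (section 6.4.2.1). With delivery at 40 weeks, as in the maximum-exposure case of section 4.2.1, pregnancy contributes 40 − 6 = 34 down to 40 − 30 = 10 weeks. Postpartum contributes 52. The postpartum share is 52/86 = 60% to 52/62 = 84%, if every woman is followed for the full 12 months.

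**Dilution.** Let p be the risk of a given preferred term in pregnancy and q its postpartum risk, equal in both arms and independent of p. The whole-study risk is 1 − (1 − p)(1 − q). The difference between arms is then (p_XR − p_SL)(1 − q), so it shrinks by exactly (1 − q).

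**Illustration.** The values of p and q are assumptions. Take p = 5% (BUP-SL) vs 15% (BUP-XR). Power is for the two-sided 5% Pearson chi-square test, by exact binomial enumeration. The 88-per-arm column corresponds to N = 176.

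| q | Whole-study risk, SL vs XR | Difference (points) | Risk ratio | Power, 100 per arm | Power, 88 per arm |
|---|---|---|---|---|---|
| Pregnancy only | 5.0% vs 15.0% | 10.0 | 3.00 | 68% | 62% |
| 1% | 6.0% vs 15.9% | 9.9 | 2.66 | 63% | 57% |
| 5% | 9.8% vs 19.3% | 9.5 | 1.97 | 49% | 43% |
| 10% | 14.5% vs 23.5% | 9.0 | 1.62 | 37% | 33% |
| 20% | 24.0% vs 32.0% | 8.0 | 1.33 | 24% | 22% |
| 40% | 43.0% vs 49.0% | 6.0 | 1.14 | 15% | 14% |

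**Unequal postpartum risk.** Keep 5% vs 15% in pregnancy and 100 per arm.

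- Postpartum 10% vs 20%: whole-study 1 − 0.95 × 0.90 = 14.5% vs 1 − 0.85 × 0.80 = 32.0%. Pooled power is 85%.
- Postpartum 5% vs 15%: 9.75% vs 27.75%. Pooled power is 92%.

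Both exceed the 68% for pregnancy alone. The pooled figure then does not show which phase or which formulation produced the difference.

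**The case against.** The strongest reply is that section 10.3.4.1 sets a minimum presentation and excludes nothing. It does not say that there will be only one table, and the whole-study window is inferred from other sections. Section 12.4 allows a soft lock after the pregnancy phase, and section 10.4.2 mentions a standalone SAP, though only for simulation details. This stands. A reader might infer that the plan requires a single pooled count, but the documents support only that no phase split is specified.

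Many harms are also outside the problem. Fetal, delivery and birth/neonatal outcomes are summarized separately by arm (sections 10.3.4.3 and 10.3.4.4), the HADS is summarized over time, and withdrawal symptoms are captured on the SOWS-Gossop (precipitated withdrawal at induction excepted). Terms confined to pregnancy are not diluted either. What remains is general maternal terms that occur in both phases.

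The size is open to challenge too. The summary is per preferred term, where a postpartum risk of 10% to 40% is high; at 1% to 5% the loss is modest at the low end. Section 4.1.2 cites postpartum treatment dropout of up to 62% by 6 months, so postpartum time at risk may be shorter than 52 weeks, although women who stop medication are encouraged to keep attending (sections 8.7.1 and 9.5).

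Three stronger readings are tempting and unsupported. One is that pooling always masks an excess in pregnancy; the unequal-risk cases above show otherwise. Another is that DSMB reports share the layout. The documents promise the DSMB AE listings, SAE summaries and expedited reports (Appendix A and section 17.3) but do not say that these use the pooled format. The third is that NMP is a stated maternal hazard. Section 4.2.1 raises it for fetal and infant effects only, and the monthly product is planned only for women not breastfeeding.

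**Conclusion.** The point holds as a gap in specification. As written, the maternal AE summary gives no pregnancy-specific rates and combines weekly with monthly BUP-XR. For terms that can occur in both phases, a pregnancy-only excess is diluted by (1 − q) when postpartum risk is equal in the arms and independent of pregnancy risk. In the illustration the loss of power ranges from 5 points (68% to 63% at q = 1%) to 53 points (68% to 15% at q = 40%). These figures rest on assumed event rates, on equal postpartum risk and on an optional test, so they show a range and are not a forecast. With a postpartum BUP-XR excess, power may rise instead, at the price of confounding phase and formulation. No primary or key secondary outcome is affected. The change is worth making because it is cheap and supplies the maternal safety information that motivates close monitoring.

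**What to change.** In section 10.3.4.1:

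- Add maternal AE and SAE tables by arm for onset (a) from randomization to delivery and (b) from delivery to 12 months postpartum.
- Within BUP-XR in (b), show counts by the formulation in use at onset (weekly or monthly). Label this split descriptive: it is not randomized, because it follows breastfeeding status and the 8 mg exception in section 9.3, and it has no BUP-SL counterpart.
- Add onset phase and formulation to the SAE listings.
- Make any Fisher or chi-square comparison within phase as well as on the pooled table, which is kept.

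The cost is a paragraph of text and some table programming. Weekly AE assessment, delivery records and injection documentation are already planned, so no visit or treatment changes. The downside is more tables with smaller counts, and more comparisons if the optional tests are run.

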10.3.5 Missing Data

Key outcomes. Illicit opioid use during pregnancy (primary outcome) and postpartum (key secondary) are based on UDS; missing UDSs will be imputed as illicit opioid-positive. The number of expected UDSs for each participant during pregnancy will depend on the length of time between randomization and delivery. UDSs are expected at the time of each weekly Medication Check Visit, thus a mother who is on study, for example, for 60 days will be expected to have had 8 UDSs. The final key secondary outcome measure, infant days of opioid treatment, is based on medical records and thus missing data should be minimal. It is possible, albeit rare, given the site selection criteria and the plan for study staff to obtain medical releases for multiple facilities, that a mother may deliver at a hospital for which medical records could not be obtained, and in this case the infant days of opioid treatment will be imputed as the worst value observed (i.e., greatest number of days). Another possible source of missing data will be if the pregnancy does not result in live birth. In this very rare case, the infant days of opioid treatment will also be imputed as the greatest number of days amongst the observed infants.

Different imputation methods, such as those loosening the missing at random assumption, may be considered to measure the sensitivity of the study results to these methods of handling missing data. Sensitivity analyses relating to the impact of the COVID-19 pandemic may be considered as well.

10.4 Sample Size Analysis

10.4.1 Parameter Selection for Calculations

The power analyses required BUP-SL group estimates for the mean and variance of the percent of UDS that are illicit opioid-negative during pregnancy. The mean selected for the sample size simulations was based on a study by Fischer and colleagues¹⁸² which found that the median percentage of urine samples negative for illicit opioids during the entire course of pregnancy was 65% for BUP-SL participants.

10.4.2 Results

Approach. Given a non-inferiority margin of 0.15, the objective of the sample size simulations was to determine whether there would be sufficient power (i.e., $\geq 80\%$) to detect that margin with a sample size of 200 participants under different assumptions regarding the impact of the three factors used in randomization. There must be sufficient power if the primary analytic model includes the randomization factors as covariates even if they are not associated with outcome. All simulated data assumed 1:1 random allocation between the treatment arms and thus one half in the BUP-XR arm and one half in the BUP-SL arm.

A simulation study was conducted to assess the power. The details of the simulation will be included in the standalone Statistical Analysis Plan. The mean in the BUP-SL arm was assumed to be 0.65 (**section 10.4.1**), and the mean in the BUP-XR arm was assumed to be 0.50 under the null, which corresponds to the specific non-inferiority margin of 0.15, and 0.65 under the alternative. The variance in both arms was fixed at 0.11, with contributions coming from the three random effects capturing randomization strata/factors and additional random error.

Results. The results of the simulations evaluating the power and type I error for the conservative case where all variance is due to random error and none due to the three random effects is given in **Table 8**. Even if the randomization factors are not associated with the outcome, there will still be *at least* 80% power to detect a 0.15 non-inferiority margin with a 2.5% significance level and a sample size of 200. Note that there is at least 80% power with a slightly lower sample size of 176 as well, meaning that the primary outcome is adequately powered with a sample size of 176.

Table 8. Power for a non-inferiority margin of 15% and a significance level of 2.5%.

Proportion of Variance due to Random Error	Mean in BUP-XR Arm	Power (%)	
		N = 176	N = 200
100%	0.50	2.7%	2.4%
	0.65	84.9%	89.0%

10.5 Descriptive Statistics

Summaries of the characteristics of the participant population in both treatment arms at screening/baseline will be prepared for the intent-to-treat participants. A summary will be prepared to show dropouts/retention over time in each treatment group. The number of missing observations will be compared between treatments.

10.6 Interim Analyses

An interim check of the parameters contributing to the initial power calculations for the BUP-SL group (mean and standard deviation for the percent opioid-negative UDS during pregnancy) will be conducted by the centralized independent DSC. The required sample size to achieve at least

80% power with a margin of 0.15 and a 2.5% type I error rate will be re-calculated. The Data and Safety Monitoring Board (DSMB) will assess whether to continue the trial with or without modification. This interim re-estimation will be implemented since these parameters are being estimated from limited repeated measures data and involve several key assumptions that impact the detectable effect size. The analysis will be conducted when approximately 100 participants (about 50 in the sublingual arm) have been randomized and have primary outcome data available (i.e., completed pregnancy portion of the active treatment phase).

A DSMB will monitor the progress of the present trial. An interim analysis could be performed to assess efficacy, futility, or safety if requested by the DSMB or NIDA. Trial monitoring guidelines for early stopping based on overwhelming benefit might be based on the Lan-DeMets approach to group sequential testing¹⁸³ with an O'Brien-Fleming-type boundary.¹⁸⁴ Such an approach does not require the number of interim looks, if any, to be specific *a priori*. The monitoring guidance for early stopping for lack of benefit or for futility might be based upon an approach of conditional probability.¹⁸⁵ Additional safety interim looks could be performed (without formal testing being performed) at the DSMB's or NIDA's request.

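### The interim sample-size check uses the outcome spread of about 50 BUP-SL women, though about 100 women in both arms will have data and the primary test depends on both variances

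*Combined protocol and SAP*

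**What the plan says.** Section 10.6 of the combined protocol and SAP describes "An interim check of the parameters contributing to the initial power calculations for the BUP-SL group", namely the mean and SD of the percent of opioid-negative urine screens in pregnancy. It takes place when "approximately 100 participants (about 50 in the sublingual arm) have been randomized and have primary outcome data available". The sample size for at least "80% power with a margin of 0.15 and a 2.5% type I error rate will be re-calculated", and the DSMB then considers whether the trial continues as it is or is modified. The stated reason is that "these parameters are being estimated from limited repeated measures data and involve several key assumptions that impact the detectable effect size". The check "will be conducted by the centralized independent DSC".

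Section 10.4.2 gives the planning values: "The variance in both arms was fixed at 0.11", and "The mean in the BUP-SL arm was assumed to be 0.65", with the same mean in BUP-XR under the alternative. Section 10.3.2 tests non-inferiority with a two-sided 95% confidence interval for the BUP-XR minus BUP-SL difference, whose lower limit must exceed -0.15. Sections 10.3.1 and 10.4.2 call 176 participants adequate, and the target is about 200. No section re-checks the BUP-XR variance or a pooled variance, and none explains the restriction to BUP-SL.

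**The concern.** With a fixed margin and equal true means, the required N depends on the variance and not on the mean. The variance that matters is the average over the two arms, because the standard error of the difference contains both. A check on BUP-SL alone has two weaknesses.

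- It is noisier than it needs to be: about 49 degrees of freedom where about 98 are available.
- It cannot respond to the BUP-XR variance. The assumption that both arms share the value 0.11 is one of the assumptions behind the power calculation, and this check cannot test it however many BUP-SL women it includes.

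At stake is the quality of the number put to the DSMB. It could call 176 enough when it is not, or ask for more women than are needed.

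**Working it through.** **Inputs.** Variance 0.11 in both arms, true difference 0 and 1:1 allocation (10.4.2); margin 0.15, 80% power and 2.5% one-sided alpha (10.6); about 50 women per arm at the check (10.6). Assumed, because the documents do not give them: a beta-shaped outcome with mean 0.65, and BUP-XR variances other than 0.11.

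**1. Reproduce Table 8.** The standard error is sqrt(4 × 0.11 / N), and power = Φ(0.15/SE - 1.960).

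- N = 176: SE = 0.0500, 0.15/SE = 3.00, power 85.1% (plan: 84.9%).
- N = 200: SE = 0.0469, 0.15/SE = 3.20, power 89.2% (plan: 89.0%).

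The plan's figures reproduce.

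**2. Required N.** N = 4 × V × (1.960 + 0.842)² / 0.15², which is about 1395.4 × V, where V is the average of the two arm variances.

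- V = 0.11: 153.5, so about 154.
- V = 0.15: 209.3, so about 209.

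**3. Noise when the arms have equal variances.** The outcome is a proportion bounded at 0 and 1, so the sampling was simulated from a beta distribution (200,000 trials, 50 women per arm). Normal-theory figures, from chi-square with 49 and 98 degrees of freedom, are given for comparison. They overstate the noise for a bounded outcome.

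| Quantity | BUP-SL only | Both arms, pooled |
|---|---|---|
| Variance 0.11: CV of recalculated N, beta | 13.9% | 9.8% |
| Variance 0.11: 95% range of N, beta | 111 to 195 | 124 to 183 |
| Variance 0.11: 95% range of N, normal | 99 to 220 | 114 to 199 |
| Variance 0.15 (209 needed): 176 found enough, beta | 10% | 4% |
| Variance 0.15 (209 needed): 176 found enough, normal | 22% | 13% |

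Under either model the CV falls by a factor of about sqrt(2).

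**4. Unequal variances.** BUP-SL is held at 0.11 and the BUP-XR value is assumed.

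| Quantity | BUP-XR 0.15 | BUP-XR 0.18 |
|---|---|---|
| V = (0.11 + BUP-XR)/2 | 0.130 | 0.145 |
| N for 80% power = 1395.4 × V | 181 | 202 |
| True power at N = 176 | 78.8% | 74.3% |
| True power at N = 200 | 83.7% | 79.5% |
| BUP-SL-only check calls 176 adequate (beta) | 86% | 86% |
| Pooled check calls 176 adequate (beta) | 36% | 7% |

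The 86% does not move because the check has no BUP-XR input; it returns about 154 on average in both columns. Power falls below 80% once the BUP-XR variance passes 2 × 176/1395.4 - 0.11 = 0.142 at N = 176, or 2 × 200/1395.4 - 0.11 = 0.177 at N = 200. Such values are possible, since the ceiling at mean 0.65 is 0.65 × 0.35 = 0.2275. The bias can also run the other way: with BUP-XR at 0.08, V = 0.095 and only about 133 are needed, so the BUP-SL figure would be too high.

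**5. Cost of ignoring treatment codes.** An overall SD absorbs any true difference. At a difference of 0.15 it adds 0.15²/4 = 0.0056 to the variance. Relative to 0.11 that is 5.1%, and N moves from 153.5 to 1395.4 × 0.1156 = 161.3. With no difference, the overall and pooled SDs performed almost identically in the simulation.

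**The case against.** The best defence is that a control-arm check yields no treatment contrast, re-examines the BUP-SL values on which planning was built (10.4.1), and is run by an independent data center that already performs the randomization (8.4) in an open-label trial. This stands as a legitimate reason, although the documents do not state it. It does not decide the matter, because an overall SD without treatment codes reveals no contrast either. Treatment codes are not a strong complaint against the present plan: the pooled within-arm SD needs them too, and it has the data center handle BUP-XR outcomes by arm.

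Several stronger readings are tempting, and the documents do not support them.

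- *That BUP-XR is more variable and the trial is underpowered.* Nothing in the documents shows a larger BUP-XR variance. At the target of about 200, a BUP-XR variance of 0.15 still leaves 83.7% power.
- *That the trial could be cut to 154 and lose power there.* The plan never proposes 154. Its figures are 176 and about 200.
- *That the check falsely reassures in about a fifth of trials when the true variance is 0.15.* That is the normal-theory 22%. A model that respects the bounds gives about 10%.
- *That this check is the only safeguard and that 0.11 has no basis.* The DSMB also reviews accumulating efficacy and outcome data (11.17.1, 17.3) and treats the recalculated N as one input, not as an automatic rule. Section 10.4.2 defers simulation details to a standalone SAP, so the lack of a source for 0.11 here does not show that none exists.
- *That the BUP-SL mean is useless.* It does not enter the N formula when the true means are equal, but it tests the 0.65 assumption and limits how large the variance of a proportion can be.

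**Conclusion.** The point holds as a low-severity improvement in efficiency. Section 10.6 is not in error, and the primary analysis is unaffected.

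Two things are firm. Using both arms cuts the CV of the recalculated N by a factor of about sqrt(2), and it brings in an arm that the check now cannot see. The noise gain is modest: under the beta model, the chance of wrongly finding 176 enough at a true variance of 0.15 falls from about 10% to 4%. The gain is larger if the variances differ, from 86% to 36% or 7% in the two cases worked above, but those cases rest on assumed BUP-XR variances. The beta shape is also an assumption. The consequence matters more if enrolment stops at 176, which tolerates a BUP-XR variance up to about 0.142, than at 200, which tolerates about 0.177.

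**What to change.** Change one sentence in 10.6 so that the recalculated N rests on all participants (about 100) with primary outcome data, in one of two ways:

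- the overall SD, computed without treatment codes. The variance is overstated by about 5% if the true difference were 0.15, and by more for a larger difference; the error is conservative; or
- the pooled within-arm SD, computed by the independent data center without reporting any treatment difference. This avoids the inflation but does use treatment codes.

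Keep the BUP-SL mean as a descriptive check on the 0.65 assumption. The timing, the data center and the data collected stay the same.
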